15.3 Causality

Causal relationship will be assessed for the clinical and data collection procedures. For SAEs this assignment should be made by the PI or delegated research nurse and the assessment confirmed by the Chief Investigator or a delegated Clinical Reviewer.

Relationship	Description	Reasonable possibility that the SAE may have been caused by the intervention?
Unrelated	There is no evidence of any causal relationship with the intervention	No
Unlikely	There is little evidence to suggest there is a causal relationship with the intervention (e.g. the event did not occur within a reasonable time after administration of the trial medication). There is another reasonable explanation for the event (e.g. the participant's clinical condition, other concomitant treatment).	No
Possible	There is some evidence to suggest a causal relationship with the intervention (e.g. because the event occurs within a reasonable time after administration of the trial medication). However, the influence of other factors may have contributed to the event (e.g. the participant's clinical condition, other concomitant treatments).	Yes
Probable	There is evidence to suggest a causal relationship and the influence of other factors is unlikely.	Yes
Definite	There is clear evidence to suggest a causal relationship and other possible contributing factors can be ruled out.	Yes

The causality assessment given by the Principal Investigator (or delegate) cannot be downgraded by the Chief Investigator (or delegate), and in the case of disagreement both opinions will be provided.

15.4 Expectedness

The Chief Investigator (or another delegated appropriately qualified individual) will assess each SAE to perform the assessment of expectedness. Expectedness decisions should not be guided by factors such as the participant population and participant history. Expectedness is not related to what is an anticipated event within a particular disease. SAEs which add significant information on specificity or severity of a known, already documented adverse event constitute unexpected events.

15.5 Reporting procedures

15.5.1 Participating Site Responsibilities

The PI (or delegated appropriately qualified doctor from the trial team) should sign and date the SAE CRF to acknowledge that he/she has performed the seriousness and causality assessments. Investigators should also report SAEs to their own health boards or trust in accordance with local practice.

A completed SAE form for all events requiring immediate reporting should be sent via email to the CTR within 24 hours of knowledge of the event. A separate form must be used to report each event, irrespective of whether or not the events had the same date of onset.

The participant will be identified only by trial number, date of birth and initials. The participant's name should not be used on any correspondence.

It is also required that sites respond to and clarify any queries raised on any reported SAEs and report any additional information as and when it becomes available through to the resolution of the event. Additionally, the CTR may request additional information relating to any SAEs and the site should provide as much information as is available to them in order to resolve these queries.

Serious Adverse Event (SAE) email address:

[contact]

Serious adverse events should be reported from randomisation, throughout the treatment period up to, and including 28 days after the participant is randomised.

An SAE form is not considered as complete unless the following details are provided:

- Full participant trial number
- An Adverse Event
- A completed assessment of the seriousness, and causality as performed by the PI (or another appropriately medically qualified doctor registered on the delegation log).

If any of these details are missing, the site will be contacted and the information must be provided by the site to the CTR within 24 hours.

All other AEs should be reported on the CRF following the CRF procedure described in Section 16.

15.5.2 The CTR responsibilities

Following the initial report, all SAEs should be followed up to resolution wherever possible, and further information may be requested by the CTR. Follow up information must be provided on a new SAE form. The CTR should continue reporting SAEs until 28 days after the participant is randomised. Once an SAE is received at the CTR, it will be evaluated by staff at the CTR and sent to the Chief Investigator (or their delegate) for an assessment of expectedness.

CTR will notify the main REC of all related and unexpected SAEs (i.e. all unexpected SARs) occurring during the study within **15** calendar days of the CI becoming aware of the event. All SAEs and SARs will be reported to the monitoring committees (TMG and TSC/IDMC) as required by the relevant committee/party. All unrelated SAEs will be reported to the TMG and TSC/IDMC, and any arising safety concerns will also be reported to the main REC as part of the annual progress report.

The CTR will not be reporting hospitalisation, prolonged hospitalisation, life threatening events or death to REC as they do not meet the criteria of an SAE in this trial. These will be reported to the IDMC for monitoring.

15.6 Urgent Safety Measures (USMs)

An urgent safety measure is an action that the Sponsor, Chief Investigator or Principal Investigator may carry out in order to protect the subjects of a study against any immediate hazard to their health or safety. Any urgent safety measure relating to this study must be notified to the Research Ethics Committee immediately by telephone, and in any event within 3 days in writing, that such a measure has been taken. USMs reported to the CTR will be handled according to CTR processes.

16 Statistical considerations

16.1 Randomisation

Individual patients with suspected sepsis will be randomised in a 1:1 ratio to either standard clinical management (control) or standard clinical management plus PCT guided assessment (intervention). We will use minimisation with NEWS2 score and site as stratification factors and a random element to reduce the risk of subversion [35]. This will be implemented in a secure 24-hour web-based randomisation programme controlled centrally by the Centre for Trials Research in Cardiff. Details of the randomisation procedure will be specified in a separate randomisation plan.

16.2 Sample size

The sample size calculation is based on two co-primary outcomes [36] :

1. 28-day mortality, for which we want to show non-inferiority of the PCT guided assessment as compared to current standard practice, using an absolute 2.5% non-inferiority margin. Assuming a 28-day mortality of 15% in patients managed as suspected sepsis treated in the ED [3, 12], this means that any increase in 28-day mortality from 15% to not more than 17.5% would be considered non-inferior. For

90% power and one-sided 5% significance level the sample size required is 7002, assuming there is no difference in 28-day mortality between arms. Our patient focus group were also consulted on the 2.5% non-inferiority margin and felt that this was acceptable if there were mechanisms to monitor trial outcomes, and if this was what was needed to provide a sample size which would ensure the trial could be completed as well as answer the research question.

2. Initiation of antibiotics treatment, for which we want to show superiority. Currently around 90% of patients managed as suspected sepsis receive antibiotics (RLBUHT, unpublished data). A reduction by 10 percentage points to 80% would be considered a success. To detect such an effect with 90% power and two-sided 5% significance level the sample size required is 532, which is substantially lower than what is needed for the non-inferiority endpoint. With 7002 patients we would be able to detect effects as small as a reduction from 90% to 87.6% prescriptions, with 90% power.

Accounting for 5% dropout, we need a total sample size of 7372. We include one interim analysis (after 50% of patients have provided data) with options to stop the trial early using group-sequential O'Brien-Fleming boundaries [37, 38]. We will consider stopping for effectiveness if:

- the PCT guided assessment is superior in terms of 28-day mortality (i.e. a significant reduction to less than 15%), or
- the PCT guided assessment is non-inferior in terms of 28-day mortality and superior in terms of initiation of antibiotics.

We will consider stopping for futility if the results of the interim analysis suggest futility for both endpoints.

The group-sequential design will increase the total maximum sample size (if the study is not stopped after the interim analysis) by just over 4% to 7676 (inflated for 5% dropout). However, the sample size will be substantially smaller if the trial does get stopped early.

The sample sizes were calculated using SAS 9.4 PROC POWER and PROC SEQDESIGN.

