3.1 Trial lay summary

Sepsis is a common, potentially life-threatening complication of infection. The optimal treatment for sepsis includes early recognition, prompt antibiotics and fluids into a vein (intravenous/IV). Currently, clinicians assess severity in patients in the Emergency Department (ED) with a scoring system based on simple to measure observations: the National Early Warning Score (NEWS2). NEWS2 helps clinicians identify the sickest patients. It is not specific and tends to over-diagnose sepsis leading to over-prescribing of antibiotics and promoting antimicrobial resistance. It is the best we have and currently used in over 70% of English hospitals. Adults with suspected sepsis fall into one of three categories: a) those looking ill needing urgent IV antibiotics and fluids within 1 hour, b) those that are unwell, but will not come to harm if IV antibiotics are not administered within 1 hour, allowing time for further assessment prior to starting antibiotics within 3 hours if required, c) those not critically unwell who may or may not need IV antibiotics. Procalcitonin (PCT), a blood test not widely used in the NHS, helps to identify bacterial infection. The National Institute for Health and Care Excellence (NICE) recommended further research on PCT testing in EDs for guiding antibiotic use in people with suspected sepsis.

In this study, we will conduct a randomised controlled trial to compare PCT-supported assessment with standard care of suspected sepsis in adults presenting to the ED, and measure whether this approach reduces prescriptions of antibiotics without increasing mortality by decreasing uncertainty in the group who may not need IV antibiotics urgently within 1 hour, or not need antibiotics at all.

Ten to 14 hospitals will take part in the study and 7676 adult patients with suspected sepsis will be randomly assigned to current standard of care or PCT-supported care. In the PCT arm, a bedside test (taking 20 minutes) is performed plus the NEWS2 assessment. Depending on the result of the PCT plus the NEWS2, patients will receive IV antibiotics and fluids within the current recommended time frame depending on severity (see Figure 1 – participant flow diagram). Doctors and patients will know what treatment arm they are in. Doctors remain free to use antibiotics outside the study guidelines using their clinical judgement in any of the

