Number of sites open	>7 5-7 <5	GO Discuss potential mitigating strategies REVIEW/STOP
Number of enrolled participants	>2000 1000-2000 <1000	GO Discuss potential mitigating strategies REVIEW/STOP
Eligible patients randomised (defined as number randomised/number screened and on screening log*)	>50% 30-50% <30%	GO Discuss potential mitigating strategies REVIEW/STOP
Consent rate (defined as number with informed consent from patient or consultee agreement/number randomised)	>85% 50-85% <50%	GO Discuss potential mitigating strategies REVIEW/STOP
Consideration of the PCT result and algorithm during clinical decision making (defined as number algorithm adhered too /number PCT result recorded)	>50% 35-50% <35%	GO Discuss potential mitigating strategies REVIEW/STOP
Ability to collect co-primary outcome data (defined as number with complete data for both co-primary outcomes/number randomised)	>90% 70-90% <70%	GO Discuss potential mitigating strategies REVIEW/STOP
Ability to collect 28- and 90-day follow up data (defined as number with complete follow up data/number randomised)	>70% 50-70% <50%	GO Discuss potential mitigating strategies REVIEW/STOP
Reduction in the % of patients treated within time windows for usual standard care (defined as Prospective usual Standard care treatment window data/Retrospective treatment window)	<10% 10-20% >20%	GO Amend processes REVIEW/STOP
Contamination/changes to usual care in control arm	Qualitative interviews	

- Screening log will only be active during periods when a research nurse is time tabled to be in the ED/admissions unit

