13.1 Recruitment rates

A feasibility questionnaire was sent out to the six lead study sites. The following numbers of patients fulfilling inclusion criteria per year were reported: Liverpool: 1800, Leeds: 2000, other sites 1000 each, Total: ~11000/year. If only 50- 70% of eligible patients provide deferred consent following randomisation, then the sample size of 7676 is easily achievable over 24 months.

Once all processes of screening and data collection are embedded at each site, we anticipate between 40 - 70 participants per month. In our projections, we have also taken seasonality into account, as the rate of infections is likely to be higher in the winter months.

14 Qualitative data collection and analysis

The qualitative work will have three components: interviews with clinicians, interviews with patients/carers, and observations of trial implementation. Findings will be used to aid understanding of the quantitative data and provide areas for improvement in processes to enhance the efficiency of the trial.

Interviews with ED clinicians

These will take place at two time points. Interview 1 will take place during the pilot phase and will be a semi-structured interview with 10-12 clinicians at <5 study sites (2-3 per site). This will explore the feasibility and acceptability of research processes and integration of the PCT algorithm into their ED setting. Interview 2 will be with clinicians towards the end of the trial when they have more experience of using the PCT algorithm and will identify barriers and facilitators to the use of the PCT test and algorithm in more detail, including reasons for varying from study guidelines.

Interviews with patients

We will conduct semi-structured interviews with patients after the 90 days follow-up point has been reached, in order to gain a detailed understanding of patients' experiences of care

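### Section 16.2 allows 5% loss, but consent follows randomisation and the protocol does not settle whether 7,676 counts patients randomised or patients left after consent; the feasibility total in section 13.1 is also mis-added.

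*Protocol*

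**What the plan says.** Section 16.2 sizes the trial on 28-day mortality: "Assuming a 28-day mortality of 15% in patients managed as suspected sepsis", "using an absolute 2.5% non-inferiority margin", and for "90% power and one-sided 5% significance level the sample size required is 7002". It then adds the only allowance for loss, "Accounting for 5% dropout, we need a total sample size of 7372", and inflates by about 4% for one interim analysis to reach 7,676.

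The lay summary (section 3.1) counts that figure at randomisation: "7676 adult patients with suspected sepsis will be randomly assigned". Section 13.1 counts it later: "If only 50- 70% of eligible patients provide deferred consent following randomisation, then the sample size of 7676 is easily achievable over 24 months". The synopsis gives 7,676 only as the planned sample size.

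Consent is deferred (sections 9.3 and 12.1). Footnote 1 to Figure 2 removes discharged patients who cannot be contacted after up to three attempts. Section 12.1 lets participants withdraw permission to use data already collected. Section 9.3 keeps the data of participants who die.

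Table 2 in section 13 defines the "Consent rate (defined as number with informed consent from patient or consultee agreement/number randomised". It gives GO above 85%, mitigation at 50-85% and review or stopping below 50%. A separate row covers complete co-primary data over number randomised: GO above 90%, mitigation at 70-90%, review or stopping below 70%.

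On feasibility, section 13.1 reports for the six lead sites: "Liverpool: 1800, Leeds: 2000, other sites 1000 each, Total: ~11000/year".

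**The concern.** In a deferred-consent trial, a randomised patient who refuses, or who cannot be reached, may contribute no data. Non-consent can therefore be a loss from the randomised total, in addition to ordinary dropout. A 5% allowance covers both only if at least 95% of randomised patients keep usable data. The protocol gives no reason to expect that, and elsewhere it contemplates or tolerates considerably lower consent.

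The two uses of 7,676 cannot both stand unless nearly everyone consents. The definition decides when recruitment stops and what power may be claimed for mortality, the endpoint that sets the size. The interim trigger has the same problem: section 16.2 ties it to half of patients having provided data, section 17.1 to half having been recruited and followed for 28 days, and section 27 to recruitment of half the sample size.

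The claim that the target is comfortably within reach also rests on a site total that does not match the site figures.

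**Working it through.** **Inputs** (section 16.2): mortality 15% in both arms, margin 0.025, one-sided alpha 5%, power 90%, 1:1 allocation, 5% dropout, one interim analysis at half the information.

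**1. Reproducing the plan's figures**

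- Fixed design: total N = 4 × 0.15 × 0.85 × (1.645 + 1.282)² / 0.025², which is 6,990 after rounding up per arm, against 7,002 stated (0.2% apart).
- Dropout: 7,002 / 0.95 = 7,371, or 7,372 in two equal arms.
- Interim: a two-look O'Brien-Fleming design with efficacy and futility boundaries has inflation 1.043, and 7,002 × 1.043 / 0.95 ≈ 7,690, against 7,676 stated (0.2% apart).
- Evaluable: 7,676 × 0.95 = 7,292, and 7,292 / 7,002 = 1.0414, the stated inflation.

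Section 16.2 is therefore correct as arithmetic, and 7,292 evaluable patients are what 90% power requires.

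**2. Power if 7,676 are randomised**

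Let R be the proportion with retained data. Then N = 7,676 × R, the equivalent fixed-design size per arm is n = N / (2 × 1.0414), and power = Φ(0.025 / √(2 × 0.1275 / n) − 1.645).

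At R = 0.85: N = 6,525, n = 3,133, standard error = √(0.255 / 3,133) = 0.00902, and power = Φ(2.771 − 1.645) = Φ(1.126) = 87%.

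| Retained | Analysed N | Power, two-look design | Power, no interim | Randomise to keep 7,292 |
|---|---|---|---|---|
| 95% | 7,292 | 90.0% | 91.1% | 7,676 |
| 90% | 6,908 | 88.6% | 89.7% | 8,103 |
| 85% | 6,525 | 87.0% | 88.2% | 8,579 |
| 70% | 5,373 | 80.8% | 82.2% | 10,418 |

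Direct integration of the two-look design gives the same two-look values. The antibiotic endpoint (90% to 80%) keeps more than 99% power even at half of 7,676, so only mortality is affected.

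**3. Number to randomise if 7,676 counts patients after consent**

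With the 5% dropout still to come, 7,292 are analysed and power is 90%. The number randomised is 7,676 / consent rate: 8,529 at 90%, 9,031 at 85%, 10,966 at 70% and 15,352 at 50%.

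**4. Feasibility sum (section 13.1)**

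- Six sites: 1,800 + 2,000 + 4 × 1,000 = 7,800 a year. A total of 11,000 would need 11,000 − 3,800 = 7,200 from the other sites, about seven sites at 1,000 rather than four.
- 24 months at 50% consent: 7,800 × 2 × 0.5 = 7,800. That exceeds 7,676 by 124, or 1.6%, and assumes every eligible patient is randomised.
- At 70%: 7,800 × 2 × 0.7 = 10,920. If only half of eligible patients are randomised (the GO boundary in Table 2) and 70% of those consent: 7,800 × 2 × 0.5 × 0.7 = 5,460.

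**The case against.** A reader might infer that the plan predicts 15-50% loss and so cannot deliver 90% power. The documents do not support that, for five reasons.

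- The 85% in Table 2 is a threshold for proceeding. Consent above 85% is compatible with 5% loss, and the 50-85% band prompts mitigation rather than describing an expectation.
- The 50-70% in section 13.1 is conditional and expressed over eligible patients, so part of the remainder might never be randomised. The same sentence treats 7,676 as reached after consent, a reading under which 90% power is kept. Taking the rate from that sentence and the count from the lay summary mixes two readings.
- Losing half the data is outside what the plan would carry forward unreviewed, because complete co-primary data below 70% of randomised leads to review or stopping.
- Non-consent is not the same as lost data. Consultee agreement counts as consent, deaths are retained, and section 12.1 also says that data collected before withdrawal remain usable.
- The lay summary looks out of date: it gives 10 to 14 hospitals, against a maximum of 20 in the synopsis and section 6.2.

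All of this limits the size of the problem. It does not remove it. Section 12.1 also offers withdrawal of data already collected, and footnote 1 to Figure 2 removes uncontactable patients outright. No other section says what 7,676 counts. Retaining deaths reduces the loss but concentrates it among survivors, so the powers above, which assume loss unrelated to outcome, are not necessarily conservative.

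On feasibility, up to 20 sites and a period to April 2024 may well make the target reachable. Section 13.1, however, argues from the six sites and 24 months, and that argument fails on its own figures.

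**Conclusion.** The point holds as an undefined count with an unjustified loss allowance, not as a demonstrated power shortfall. The 5% allowance matches the stated 90% power only if at least 95% of whatever 7,676 counts are analysable. If it counts randomised patients, power is about 89% at 90% retained, 87% at 85% and 81% at 70%. If it counts patients with retained data, power stands, but the number to randomise is larger and unstated: roughly 9,031 at 85% consent and 10,966 at 70%. These figures assume 15% mortality in both arms, the fixed 2.5-point margin and loss unrelated to outcome. The protocol gives no forecast of retention, so the range is shown rather than a single value.

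The feasibility total is a plain addition error, 7,800 against about 11,000. It does not affect power, but it removes the support for calling the target easy to reach from those sites in 24 months at the lower consent rate.

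**What to change.** Choose one definition and use it in the synopsis, the lay summary, and sections 13.1, 16.2, 17.1 and 27:

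- Either state that 7,676 and the 50% interim trigger count patients whose data are retained (patient consent, consultee agreement or death), and report the number randomised separately.
- Or keep 7,676 as the number randomised, replace or justify the 5% against the consent assumptions, and restate power at the observed retention.

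In section 13.1, correct the annual total from about 11,000 to about 7,800 for the six sites, and redo the projection with the current number of sites and trial period.

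The cost is wording and restated figures. The downside depends on the choice: under the first, the stated number to randomise rises; under the second, the stated power becomes somewhat less favourable.

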16.3 Missing, unused & spurious data

Missing primary outcome data is likely to be minimal, so complete case analysis will be used. However, if this exceeds more than 20% of participants we will employ multiple imputation and report the impact on the treatment effect alongside the complete case analysis. Further detail is provided in the PRONTO Statistical Analysis Plan (SAP).

